# **3. ENDPOINTS AND BASELINE VARIABLES: DEFINITIONS AND CONVENTIONS**

## 3.1. Primary Endpoints

## 3.1.1. Primary Safety Endpoints

- Local reactions (pain at the injection site, redness, and swelling) within 7 days after each dose in each vaccine group.
- Systemic events (fever, vomiting, diarrhea, headache, fatigue, chills, new or worsened muscle pain, and new or worsened joint pain) within 7 days after each dose in each vaccine group.
- AEs from Dose 1 to 1 month after Dose 2.
- SAEs from Dose 1 to 12 months after Dose 2.

# 3.1.1.1. Local Reactions

The local reactions assessed and reported in the e-diary are redness, swelling, and pain at the injection site, from Day 1 through Day 7 after each dose, where Day 1 is the day of each dose. This section describes derivations with details for the assessment of local reactions: presence, severity level, duration, and onset day.

#### Presence or Absence

For the data summary of the presence (yes or no) of a local reaction during the interval from Day 1 through Day 7 for each dose, where Day 1 is the day of each dose, the following variables are required in order to compute the proportions:

- Presence (yes or no) of each severe/Grade 4 local reaction on each day and any day (Day 1 through Day 7);
- Presence (yes or no) of each local reaction by maximum severity on any day (Day 1 through Day 7).

For each local reaction and any local reaction on any day, Table 3 explains the algorithm to derive the presence of a reaction (yes or no) during the interval from Day 1 through Day 7, where Day 1 is the day of each dose.

Variable a	Yes (1)	No (0)	Missing (.)
Presence of each local reaction.	Participant reports the reaction as "yes" on any day (Day 1 through Day 7).	Participant reports the reaction as "no" on all 7 days (Day 1 through Day 7) or as a combination of "no" and missing on all 7 days (Day 1 through Day 7).	Participant does not report any data on all 7 days (Day 1 through Day 7) for the reaction.
Presence of any local reaction.	Participant reports any local reaction as "yes" on any day (Day 1 through Day 7).	For all 3 local reactions, participant reports "no" on all 7 days (Day 1 through Day 7) or as a combination of "no" and missing on all 7 days (Day 1 through Day 7).	Participant does not report any data for all 3 local reactions on all 7 days (Day 1 through Day 7).

# Table 3.Derived Variables for Presence of Each and Any Local Reaction Within7 Days for Each Dose

a. The variables will be derived for each and any of the local reactions (redness, swelling, and pain at the injection site) and for each and any of the severe local reactions within the interval from Day 1 through Day 7 after each dose.

# Severity and Maximum Severity

Redness and swelling will be measured and recorded in measuring device units (range: 1 to 21) and then categorized during analysis as absent, mild, moderate, or severe based on the grading scale in Table 4. Measuring device units can be converted to centimeters according to the following formula: 1 measuring device unit = 0.5 cm. Pain at the injection site will be assessed by the participant as absent, mild, moderate, or severe according the grading scale in Table 4.

	Mild (Grade 1)	Moderate (Grade 2)	Severe (Grade 3)	Potentially Life Threatening (Grade 4)
Pain at the injection site	Does not interfere with activity.	Interferes with activity.	Prevents daily activity.	Emergency room visit or hospitalization for severe pain.
Redness	>2.0 cm to 5.0 cm (5 to 10 measuring device units).	>5.0 cm to 10.0 cm (11 to 20 measuring device units).	>10 cm (≥21 measuring device units).	Necrosis or exfoliative dermatitis.
Swelling	>2.0 cm to 5.0 cm (5 to 10 measuring device units).	>5.0 cm to 10.0 cm (11 to 20 measuring device units).	
 
>10 cm
 
(≥21 measuring device units).
 
	Necrosis.

 Table 4.
 Local Reaction Grading Scale

For each local reaction reported for each dose, the maximum severity grade will be derived for the e-diary collection period (Day 1 through Day 7, where Day 1 is the day of each dose) as follows:

Maximum severity grade = highest grade (maximum severity) within 7 days after vaccination (Day 1 through Day 7) among severity grades where the answers are neither "no" nor missing for at least 1 day during the interval from Day 1 through Day 7.

#### Duration (First to Last Day Reported)

For participants experiencing any local reactions (or those with a derived reaction as described in Table 4), the maximum duration (last day of reaction – first day of reaction + 1) will be derived for each study vaccination. Resolution of the reaction is the last day on which the reaction is recorded in the e-diary or the date the reaction ends if it is unresolved during the participant e-diary recording period (end date collected on the CRF), unless chronicity is established. If there is no known end date, the duration will be considered unknown and set to missing. However, if a reaction is ongoing at the time of a subsequent vaccination, the end date/day for the ongoing event would be the date/day that the next vaccine is administered, which will be used for the duration computation. Participants with no reported reaction have no duration.

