Review ongoing reactogenicity e-diary symptoms and obtain stop dates					X	X	X					
Collect AEs and SAEs as appropriate e	X	X	X	X	X	X	X	X	X	X	X	X
Collect e-diary or assist the participant to delete application										X		

Visit Number	Screening	1	2	3	4	5	6	7	8	9	Unplanned	Unplanned
Visit Description	Screening	Vax 1	Next-Day Follow- up Visit (Vax 1)	1-Week Follow- up Visit (Vax 1)	Vax 2	1-Week Follow- up Visit (Vax 2)	2-Week Follow- up Visit (Vax 2)	1-Month Follow- up Visit	6-Month Follow- up Visit	12- Month Follow- up Visit	Potential COVID-19 Illness Visit a	Potential COVID-19 Convalescent Visit a
Visit Window (Days)	0 to 28 Days Before Visit 1	Day 1	1 to 3 Days After Visit 1	6 to 8 Days After Visit 1	19 to 23 Days After Visit 1	6 to 8 Days After Visit 4	12 to 16 Days After Visit 4	28 to 35 Days After Visit 4	ONLY THO PARTIC ORIGI ASSIGN BNT16 PLAC RECIP WHO D	350 to 378 Days After Visit 4 7 FOR OSE CIPANTS NALLY NED TO 2b2 OR CEBO PIENTS ECLINE 162b2	Optimally Within 3 Days After Potential COVID-19 Illness Onset	28 to 35 Days After Potential COVID-19 Illness Visit
Collection of local test result of COVID-19 and local diagnosis of COVID-19											X	

Abbreviation: vax = vaccination.

- a. The COVID-19 illness visit may be conducted as a telehealth visit.
- b. Including, if indicated, a physical examination.
- c. Hematology: hemoglobin, hematocrit, complete blood count with differential, and platelets. Blood chemistry: alanine aminotransferase (ALT), aspartate aminotransferase (AST), alkaline phosphatase, total bilirubin, blood urea nitrogen (BUN), and creatinine.
- d. Prior to vaccination, if at a vaccination visit.
- e. Details of AE and SAE reporting are described in Section 8.3.1.

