# 6.1.1.1.2. Supplementary Analyses

To support the assessment of local reactions, the following endpoints (as defined in Section 3.1.1.1) will be summarized with the same analysis time point and analysis population, analysis methodology, and appropriate reporting results. Confirmed e-diary errors will be excluded from these analyses.

- Duration (days) of each local reaction after each dose.
- Onset day of each local reaction after each dose.

These continuous endpoints will be summarized by displaying n, mean, median, standard deviation, minimum, and maximum for each vaccine group.

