# 6.1.1.2.2. Supplementary Analyses

The following endpoints for assessment of systemic events will be summarized similarly to the assessment of local reactions:

- Duration of each systemic event after each dose.
- Onset day of each systemic event after each dose.

These continuous endpoints will be summarized by displaying n, mean, median, standard deviation, minimum, and maximum for each vaccine group.

The use of antipyretic medication (see Section 3.1.1.3) will be summarized similarly to systemic events, except that there is no severity level associated with the use of antipyretic medication.

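### Reaction durations with no end date are set to missing, while Dose 1 durations are cut at Dose 2: a possible downward bias, different by dose, in a supplementary summary

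*SAP*

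**What the plan says.** SAP 3.1.1.1, under Duration, gives the formula: "the maximum duration (last day of reaction – first day of reaction + 1) will be derived for each study vaccination". A reaction that outlasts the diary takes its end date from the CRF, "unless chronicity is established"; the SAP neither defines chronicity nor says what duration such a reaction then receives. Two further rules cover unresolved reactions:

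- No end date: "If there is no known end date, the duration will be considered unknown and set to missing".
- Still present at the next dose: "the end date/day for the ongoing event would be the date/day that the next vaccine is administered", and that date enters the calculation.

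SAP 3.1.1.2 and 3.1.1.3 carry the derivations over to systemic events and, where applicable, antipyretic use. The outputs are "Duration (days) of each local reaction after each dose" (SAP 6.1.1.1.2) and "Duration of each systemic event after each dose" (SAP 6.1.1.2.2), both supplementary and summarised by n, mean, median, standard deviation, minimum and maximum. No censoring method is given.

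On data capture, the Protocol schedule has the row "Review ongoing reactogenicity e-diary symptoms and obtain stop dates". It is marked at Visits 4, 5 and 6 for the clinical laboratory subset (1.3.1). The matching row for standard participants is marked at Visits 2, 3 and 4 (1.3.2). In both cases these are the Dose 2 visit and the visits 1 and 2 weeks after it. The 1-month visit lists (8.11.1.8 and 8.11.2.5) contain no diary or stop-date step. Protocol 8.2.2 nevertheless obliges the investigator or designee to obtain stop dates for anything ongoing on the last diary day, with no time limit. Section 8.2.2.2 also asks participants to report local reactions that go on past the diary.

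**The concern.** Short reactions close inside the 7-day diary. A reaction that outlasts the diary has a duration only if someone obtains an end date. Missingness therefore depends on the quantity being measured, and it removes reactions for which a lower bound is already known. The same clinical course is also treated differently by dose: after Dose 1 it can be stored as a completed value it did not have, and after Dose 2 it can vanish. A tolerability table read for how long reactions last, and how long the longest lasted, could then understate both, and the two doses would not be compared on like terms.

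**Working it through.** The documents give no duration figure, no share of prolonged reactions and no rate of unobtained stop dates, so there is no stated number to reproduce. The date arithmetic below comes from the documents. The effect on the mean rests on assumed inputs.

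**1. Ceilings by dose.** Inputs: Dose 2 falls 19 to 23 days after Dose 1; the 2-week visit is 12 to 16 days after Dose 2; the 1-month visit is 28 to 35 days after Dose 2. Take onset on the day of dosing (Day 1) and use last day − first day + 1.

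- A Dose 1 reaction ongoing at Dose 2 ends on Day 20 to 24, so the stored value is 20 − 1 + 1 = 20 to 24 − 1 + 1 = 24 days. This holds even if the true end date is later obtained.
- After Dose 2, the last scheduled stop-date review falls on Day 13 to 17, so the longest duration it can close is 13 to 17 days. Beyond that, the value depends on the general duty in Protocol 8.2.2 and on participant reporting.

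A 30-day reaction is therefore stored as 20 to 24 days after Dose 1. After Dose 2 it is stored as 30 days if the date is obtained and as missing if not, even though the 2-week visit had already shown it to have lasted at least 13 days.

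**2. Effect on the mean (assumed inputs).** Let a share p of reactions last L days and the rest average m days. The true mean is (1 − p)m + pL. With a 21-day interval the Dose 1 value is cut at 22 days, so for L above 22 the Dose 1 error is −p(L − 22). If a fraction f of the long reactions has no end date, the Dose 2 mean is [(1 − p)m + p(1 − f)L] / (1 − pf). At f = 1 the error is −p(L − m).

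Example: p = 2%, L = 30, m = 2.5.

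- True mean: 0.98 × 2.5 + 0.02 × 30 = 3.05.
- Dose 1: 0.98 × 2.5 + 0.02 × 22 = 2.89, error −0.16.
- Dose 2, f = 0: 3.05, no error.
- Dose 2, f = 0.25: (2.45 + 0.45) / 0.995 = 2.91.
- Dose 2, f = 0.5: (2.45 + 0.30) / 0.99 = 2.78.
- Dose 2, f = 1: 2.45 / 0.98 = 2.50, error −0.55.

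Which dose looks shorter thus depends on how many stop dates are obtained.

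Range: with p from 1% to 5%, L from 20 to 60 and m from 2 to 3, the Dose 1 mean is 0 to 1.9 days too low (largest: 0.05 × 38). The Dose 2 mean at f = 1 is 0.17 to 2.9 days too low (0.01 × 17 to 0.05 × 58). Even if all 120 vaccine recipients reported a reaction, 1% to 5% is only about 1 to 6 people, so the maximum can turn on a single participant.

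**3. Effect on the median (assumed lognormal durations, median 2 days before rounding up, log-scale SD 0.6, 0.9 and 1.2).** Cutting at 22 days left the median unchanged. Dropping everything over 15 days moved it by 0 to 1 day, while the mean fell from 2.89 to 2.89, from 3.50 to 3.26 and from 4.62 to 3.46.

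**The case against.** The strongest reply is that the schedule is not the whole capture system. Protocol 8.2.2 makes stop dates mandatory with no cut-off, and 8.2.2.2 has participants report persisting local reactions. Section 8.12 requires ongoing reactions flagged as Grade 3 or suspected Grade 4 to be assessed at the next study visit when an unscheduled visit was not possible or not judged necessary. The 1-month visit is a contact at which the 8.2.2 duty still applies. A missing duration therefore needs that duty to go unmet, or a reaction with no end to record. This stands, and it rules out three stronger readings that a reader might infer:

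- That the longest reactions drop out as a consequence of the plan. They drop out only where no end date is obtained.
- That Dose 1 reactions ongoing at Dose 2 are lost. They stay in, truncated, and can supply the reported maximum.
- That a reaction judged chronic is set to missing. The SAP makes an exception for it and attaches no result.

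It is also fair that ending a Dose 1 reaction at Dose 2 is an attribution convention, since later symptoms cannot be cleanly assigned to the first injection. That is a reason to stop counting at Dose 2; it does not make the value a completed duration. Finally, the planned n, set against the number of participants with the reaction, shows how many durations are missing. It does not show how many were truncated or how long the missing ones are known to have lasted.

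**Conclusion.** The point holds in a limited form. A known minimum duration is discarded wherever no end date is obtained, and the rule for unresolved reactions differs by dose. The cut at Dose 2 operates even with perfect stop-date collection; the loss after Dose 2 is conditional. Because the reactions at risk are those that outlast the diary, any bias is downward. It acts mainly on the mean and maximum and hardly on the median.

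Its size cannot be computed from the documents. Under the assumed inputs the Dose 2 mean ranges from unbiased, if every date is obtained, to a few tenths of a day too low in the central example, and more only if prolonged reactions are both commoner and much longer. Duration is a supplementary description in a study with no hypotheses. Presence of reactions, maximum severity and the primary percentages do not use it.

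**What to change.** Amend SAP 3.1.1.1 so that a reaction with no end date, or still ongoing at the next dose, is right-censored at the last date it was known to be ongoing. For a Dose 1 reaction ongoing at Dose 2, that is the Dose 2 date. Use one rule for both doses, define chronicity and place chronic reactions under the same rule. Apply it to systemic events and antipyretic use as well.

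In the tables of SAP 6.1.1.1.2 and 6.1.1.2.2, report per dose and vaccine group the number of durations censored or truncated and the longest known minimum duration. Put a Kaplan-Meier median beside the planned statistics. With few censored values that median will be close to the planned one, so the counts and the longest known minimum carry most of the added information.

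If any 1-month visits remain, align their stop-date step with Protocol 8.2.2. This is probably too late: Amendment 3 places the unblinding contact after that visit, and the current SAP is dated 18 November 2021. The SAP part does not depend on it. The cost is SAP wording, a little programming, and a footnote or column in the duration tables.

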#### Onset Day

The onset day of each local reaction will be derived. Onset day is defined as the first day of reporting any severity.

For the onset day of each local reaction, if participants report change in severity of the local reaction, only the first day of reporting that specific local reaction will be counted.

# 3.1.1.2. Systemic Events (Systemic Event Symptoms and Fever)

The systemic events assessed and recorded in the e-diary are fatigue, headache, chills, vomiting, diarrhea, new or worsened muscle pain, and new or worsened joint pain from Day 1 through Day 7, where Day 1 is the day of each dose. The derivations for systemic events will be handled in a way similar to the way local reactions are handled for presence of event, severity level, duration, and onset day.

The variables associated with the systemic events will be computed in a way similar to the way local reactions are computed (see Section 3.1.1.1). Maximum temperature range over the period from Day 1 through Day 7 will be mapped into the ranges described in Table 6 for summary of maximum temperature.

The symptoms will be assessed by the participant as absent, mild, moderate, or severe according to the grading scale in Table 5.

	Mild (Grade 1)	Moderate (Grade 2)	Severe (Grade 3)	Potentially Life Threatening (Grade 4)
Vomiting	1-2 times in 24 hours.	>2 times in 24 hours.	Requires IV hydration.	Emergency room visit or hospitalization for hypotensive shock.
Diarrhea	2 to 3 loose stools in 24 hours.	4 to 5 loose stools in 24 hours.	6 or more loose stools in 24 hours.	Emergency room visit or hospitalization for severe diarrhea.
Headache	Does not interfere with activity.	Some interference with activity.	Prevents daily routine activity.	Emergency room visit or hospitalization for severe headache.
Fatigue/tiredness	Does not interfere with activity.	Some interference with activity.	Prevents daily routine activity.	Emergency room visit or hospitalization for severe fatigue.
Chills	Does not interfere with activity.	Some interference with activity.	Prevents daily routine activity.	Emergency room visit or hospitalization for severe chills.
New or worsened muscle pain	Does not interfere with activity.	Some interference with activity.	Prevents daily routine activity.	Emergency room visit or hospitalization for severe new or worsened muscle pain.
New or worsened joint pain	Does not interfere with activity.	Some interference with activity.	Prevents daily routine activity.	Emergency room visit or hospitalization for severe new or worsened joint pain.

 Table 5.
 Systemic Event Grading Scale

Abbreviation: IV = intravenous.

Oral temperature will be collected in the evening, daily, for 7 days following each dose (Days 1 through 7, where Day 1 is the day of each dose) and at any time during the 7 days that fever is suspected. Fever is defined as an axillary temperature of  $\geq$ 37.5°C. The highest temperature for each day will be recorded in the e-diary. Temperature will be measured and recorded to 1 decimal place. Fever will be grouped into ranges for the analysis according to Table 6 below.

#### Table 6.Scale for Fever

≥37.5°C to 38.4°C	
>38.4°C to 38.9°C	
>38.9°C to 40.0°C	
>40.0°C	

Note: Fever is defined as axillary temperature  $\geq$  37.5°C.

# 3.1.1.3. Use of Antipyretic Medication

The use of antipyretic medication is also recorded in the e-diary from Day 1 through Day 7, where Day 1 is the day of each dose. For the use of antipyretic medication from Day 1 through Day 7 after each dose, the following endpoints and variables will be derived for analysis following the same rules as for local reactions (see Section 3.1.1.1), where applicable.

- Presence (yes or no) of use of antipyretic medication on each day (Day 1 through Day 7);
- Presence (yes or no) of use of antipyretic medication on any day (Day 1 through Day 7);
- Duration (first to last day reported) of use of antipyretic medication;
- Onset day of use of antipyretic medication.

The use of antipyretic medication will be summarized and included in the systemic event summary tables but will not be considered a systemic event.

## 3.1.1.4. Adverse Events

AEs will be assessed from the time of informed consent through 1 month after Dose 2.

The primary endpoint "AEs from Dose 1 to 1 month after Dose 2" and other AE endpoints will be summarized by SOC and PT at the participant level.

This primary endpoint will be supported by summaries and listings of related AEs, severe AEs, and immediate AEs (within the first 30 minutes after each dose).

AE reporting will be based on the specific reporting period. Standard algorithms for handling missing AE dates will be applied as described in the Pfizer Vaccine data standard rules.

A 3-tier approach will be used to summarize AEs. Under this approach, AEs are classified into 1 of 3 tiers. Different analyses will be performed for different tiers:

- Tier 1 events: These are prespecified events of clinical importance and are identified in a list in the product's safety review plan.
- Tier 2 events: These are events that are not Tier 1 but are considered "relatively common." A MedDRA PT is defined as a Tier 2 event if there are at least 4 of participants with the AE term in at least 1 vaccine group.
- Tier 3 events: These are events that are neither Tier 1 nor Tier 2.

Confirmed COVID-19 diagnosis (SARS-CoV-2 positive test) will be collected as an AESI from the time the participant provides informed consent until study completion (Month 12 (Visit 9) for the clinical laboratory subset, Month 12 (Visit 7) for standard participants).

# 3.1.1.5. Serious Adverse Events

SAEs will be collected from the time the participant provides informed consent to approximately 12 months after Dose 2 of study intervention.

The safety endpoint "SAEs from Dose 1 to 12 months after Dose 2" will be summarized by SOC and PT at the participant level.

# 3.1.1.6. Hematology and Chemistry Laboratory Parameters

For the clinical laboratory subset, below are the additional primary safety endpoints:

- Abnormal hematology and chemistry laboratory values 1 and 7 days after Dose 1; and 7 days after Dose 2.
- Grading shifts in hematology and chemistry laboratory assessments between baseline and 1 and 7 days after Dose 1; and before Dose 2 and 7 days after Dose 2.

The following safety laboratory tests will be performed at the times defined in the protocol, Section 1.3 (schedule of activities). Additional laboratory results may be reported on these samples as a result of the method of analysis or the type of analyzer used by the clinical laboratory, or as derived from calculated values. These additional tests would not require additional collection of blood. Unscheduled clinical laboratory measurements may be obtained at any time during the study to assess any perceived safety issues.

Hematology	Chemistry
Hemoglobin	BUN and creatinine
Hematocrit	AST, ALT
RBC count	Total bilirubin
MCV	Alkaline phosphatase
MCH	
MCHC	
Platelet count	
WBC count	
Total neutrophils (Abs)	
Eosinophils (Abs)	
Monocytes (Abs)	
Basophils (Abs)	
Lymphocytes (Abs)	

Clinically significant abnormal laboratory findings should be recorded in the AE CRF in accordance with the following grading scale (Table 7). Additionally, the primary criterion for abnormality will follow the Pfizer safety rule book.

Hematology	Mild (Grade 1)	Moderate (Grade 2)	Severe (Grade 3)	Potentially Life Threatening (Grade 4)
Hemoglobin	11.0 - 12.0	9.5 - 10.9	8.0 - 9.4	<8.0
(Female) - g/dL				
Hemoglobin	12.5 - 13.5	10.5 - 12.4	8.5 - 10.4	<8.5
(Male) - g/dL				
WBC increase - cells/mm 	10,800 - 15,000	15,001 - 20,000	20,001 - 25,000	>25,000
WBC decrease - cells/mm 	2500 - 3500	1500 - 2499	1000 - 1499	<1000
Lymphocytes decrease - cells/mm 	750 - 1000	500 - 749	250 - 499	<250
Neutrophils decrease - cells/mm 	1500 - 2000	1000 - 1499	500 - 999	<500
Eosinophils - cells/mm 	650 - 1500	1501 - 5000	>5000	Hypereosinophilic
Platelets decreased - cells/mm 	125,000 - 140,000	100,000 - 124,000	25,000 - 99,000	<25,000
Chemistry	Mild (Grade 1)	Moderate (Grade 2)	Severe (Grade 3)	Potentially Life Threatening (Grade 4)
BUN - mg/dL	23 - 26	27 - 31	>31	Requires dialysis
Creatinine - mg/dL	1.5 – 1.7	1.8 - 2.0	2.1 - 2.5	>2.5 or requires dialysis
Alkaline phosphate - increase by factor	$1.1 - 2.0 \times ULN$	$2.1 - 3.0 \times ULN$	$3.1 - 10 \times ULN$	>10 × ULN
Liver function tests - ALT, AST increase by factor	1.1 – 2.5 × ULN	2.6 – 5.0 × ULN	5.1 – 10 × ULN	>10 × ULN
Bilirubin - when accompanied by any increase in liver function test - increase by factor	1.1 – 1.25 × ULN	1.26 – 1.5 × ULN	1.51 – 1.75 × ULN	>1.75 × ULN
Bilirubin - when liver function test is normal - increase by factor	1.1 – 1.5 × ULN	1.6 – 2.0 × ULN	2.0 – 3.0 × ULN	>3.0 × ULN

 Table 7.
 Laboratory Abnormality Grading Scale

Abbreviations: ALT = alanine aminotransferase; AST = aspartate aminotransferase; BUN = blood urea nitrogen; ULN = upper limit of normal; WBC = white blood cell.

